#### **3.1.3 Exploratory Endpoints**

- Median duration of OS

## **3.2 Safety**

### **3.2.1 Definitions**

#### **3.2.1.1 Adverse Events**

An AE is any unfavorable and unintended sign (including an abnormal laboratory finding), symptom, or disease temporally associated with the use of a medical treatment or procedure that may or may not be considered related to the medical treatment or procedure. Assessment of the occurrence of an AE will be based on changes in the patient's physical examination, laboratory results, and/or signs and symptoms. An AE also includes any newly occurring event or previous condition that has increased in severity or frequency from signing the informed consent.

Adverse events will be monitored until they are resolved or clearly determined to be due to a patient's stable or chronic condition or intercurrent illness(es). Medical care will be provided, as defined in the informed consent, for any AE related to study participation.

### ***3.2.1.2 Serious Adverse Event***

A serious adverse event (SAE) is any untoward medical occurrence resulting in the following:

- Death
- Is life-threatening (defined as an event in which the patient was at risk of death at the time of the event; it does not refer to an event which hypothetically might have caused death if it were more severe)
- Requires in-patient hospitalization or causes prolongation of existing hospitalization
- Results in persistent or significant disability/incapacity
- Is a congenital anomaly/birth defect
- Is an important medical event (defined as a medical event(s) that may not be immediately life-threatening or result in death or hospitalization, but, based upon appropriate medical and scientific judgment, may jeopardize the patient or may require intervention [e.g., medical or surgical] to prevent 1 of the other serious outcomes listed in the definition above). Examples of such events include, but are not limited to, intensive treatment in an emergency room or at home for allergic bronchospasm; blood dyscrasias or convulsions that do not result in hospitalization.

Although overdose is not always serious by regulatory definition, this event should be reported on an SAE form and sent to the sponsor in an expedited manner.

All pregnancies, regardless of outcome, must be reported to the sponsor on a pregnancy form, not an SAE form.

***NOTE:***

The following hospitalizations are not considered SAEs in sponsor clinical studies:

- A visit to the emergency room or other hospital department lasting <24 hours, that does not result in admission (unless considered "important medical event" or event that is "life-threatening")
- Elective surgery planned prior to signing consent
- Admissions as per protocol for a planned medical/surgical procedure
- Routine health assessment requiring admission for pretreatment assessment/trending of health status (e.g., routine colonoscopy)

- Medical/surgical admission for purpose other than remedying ill health state and was planned prior to signing consent. Appropriate documentation is required in these cases
- Admission encountered for another life circumstance that carries no bearing on health status and requires no medical/surgical intervention (e.g., lack of housing, economic inadequacy, care-giver respite, family circumstances, administrative)
- Admission for PD

### **3.2.2      Period of Observation**

All AEs (including SAEs) regardless of the relationship to study drug or study procedure will be collected from obtaining informed consent to the EoT assessment. At EoT, Grade  $\geq 2$  AEs considered to be at least possibly related to the study drug must be followed up after the EoT assessment until the events have recovered to Grade  $\leq 1$ , returned to the baseline level, are judged by the investigator to be stabilized, or to be given a reason that further follow-up will not be required (See [Section 2.6.4](#)). However, if patient begins to receive new cancer therapy or withdraws consent to study participation, no further follow-up will be conducted. The outcome of the events which do not resolve by that time will be recorded as “ongoing” on the eCRF.

### **3.2.3      Pre-existing Conditions**

A pre-existing condition will not be reported as an AE unless the condition worsens by at least 1 CTCAE Grade during the study. However, the pre-existing condition must be recorded in the screening eCRF as a pre-existing condition, and all concomitant medication administered for the condition must be recorded as concomitant medication in the eCRF following guidelines for other concomitant medication.

### **3.2.4      Documentation and Reporting of Adverse Events by Investigator**

Any signs and symptoms that occur after obtaining the informed consent will be described as AEs and graded according to the CTCAE in the AE section of the eCRF.

Abnormal laboratory values will be recorded on the laboratory section of the eCRF and not in the AE section. Abnormal laboratory results leading to a clinical diagnosis will be reported with a clinical term by the investigator and recorded in the AE section of the eCRF in addition to the laboratory section. Abnormal laboratory results that meet the definition of an SAE should also be reported on an SAE form. Relationship (reasonable causal relationship) to drug treatment and countermeasures taken will be noted on the eCRF. Investigators must record in the eCRF their opinion concerning the relationship of the AE to study therapy.

Progressive disease should not be recorded as an AE. Diagnostic and therapeutic non-invasive and invasive procedures, such as surgery, will not be reported as an AE, but the procedure and/or therapeutic treatment should be recorded on the appropriate eCRF. The medical condition for which the procedure was performed must be reported.

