## 1.8 Dose Selection and Risk Assessment

A Phase 1 dose finding study of HBI-8000 has been conducted in Japan in NHL patients. Based on the clinical experience from China (Section 1.6) where the CFDA approved dose of HBI-8000 is 30 mg BIW, the starting dose of this study was 30 mg. Data to date have shown that both 30 mg and 40 mg dose levels were well tolerated. The Grade 3 and 4 toxicities observed at 40 mg in 2 out of 6 patients were transient, and asymptomatic. The Grade 4 neutropenia was asymptomatic resolved promptly with administration of Granulocyte-colony stimulating factor (G-CSF). The Grade 3 ALT elevation was also asymptomatic resolved with dosing interruption. On the other hand, strong signals of efficacy were observed at 40 mg as evidenced by none of the seven patients showing disease progression and 5 achieving partial response (PR). Furthermore, 4 of the 5 patients with R/R ATL enrolled in this Phase 1 study achieved PR, 1 had stable disease (SD). Although the sample size is small and firm conclusion must not be made, it is worth pointing out that the 4 PRs were observed in ATL patients initially treated at 40 mg while the SD patient were treated at 30 mg. Thus, it was felt that such an efficacy signal in patients with strong unmet medical needs warrants further investigation. Upon review of risk and benefit in totality, the 40 mg BIW schedule was selected as the starting dose for the Phase 2. The current study is designed to further evaluate the efficacy of HBI-8000 in R/R ATL.

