#### **Safety Endpoints:**

Safety and tolerability of HBI-8000 will be measured by the number of patients with AEs and severity of AEs as defined by Common Terminology Criteria for Adverse Events (CTCAE) version 4.03. Adverse events reported by the patients or observed during physical examination, vital signs assessments, ECGs, and laboratory tests results will be recorded and assessed by severity and association with study treatment.

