**Table 1: HBI-8000 Tablet Dosage Adjustment Guidelines**

AE Category	AE Description	Dosage interruption with/without Reduction
Hematological Adverse Events-- Uncomplicated	

• Neutropenia Grade 3 or 4 upon observation

• Thrombocytopenia Grade 3 or 4 upon observation

	Hold dose, initiate G-CSF, once resolved to $\leq 1$ within 2 weeks, resume at same dose.  Hold dose, once resolved to $\leq 1$ within 2 weeks, resume at same dose.  If recovery takes $>2$ weeks, discontinue study drug.
Hematological Adverse Events-- Complicated	

• Grade 4 afebrile neutropenia <math>> 7</math> days despite optimal growth factor support

• Grade <math>\geq 3</math> febrile neutropenia or neutropenic infection

• Grade <math>\geq 3</math> thrombocytopenia with clinically significant bleeding or Grade <math>\geq 3</math> thrombocytopenia requiring a platelet transfusion

	Hold doses, once resolved to $\leq 1$ within 2 weeks, resume at reduced dose (from 40 mg to 30 mg, or from 30 mg to 20 mg);  If recovery takes $> 2$ weeks, discontinue study drug.
Non-Hematological Adverse Events (excluding laboratory values without clinical significance)	Grade 3	Hold doses, once resolved to $\leq 1$ within 2 weeks, resume at reduced dose (from 40 mg to 30 mg, or from 30 mg to 20 mg), with appropriate prophylaxis as applicable.  If recovery takes $>2$ weeks, discontinue study drug.
	Grade 4	Discontinue study drug

The G-CSF is recommended to be prescribed when uncomplicated Grade 3 or 4 neutropenia is observed. Patient management should follow institution guidelines and be recorded in eCRFs. Laboratory tests should be obtained at least once a week to monitor recovery.

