### **5.10.1 Adverse Events**

AEs will be classified using the MedDRA classification system version 19.0 or higher. The severity of the toxicities will be graded according to the NCI CTCAE version 4.03.

In all summaries, emphasis will be placed on treatment-emergent adverse events (TEAEs), namely, those with initial onset or that worsen in severity after the first dose of HBI-8000. TEAEs will be summarized by the frequency of patients experiencing TEAEs corresponding to body systems and MedDRA preferred term and by worst NCI CTCAE (version 4.03) Grade. Summaries will also be provided of treatment-related TEAEs, namely, those judged by the investigator to be related or likely related to HBI-8000.

TEAEs resulting in discontinuation of HBI-8000 treatment or withdrawal from the study, Grade 3 or higher, SAEs, and deaths on-study will be tabulated.

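### Section 3.2.4's rule for laboratory abnormalities conflicts with the AE definition and Table 1, so asymptomatic laboratory toxicities could be missing from, or unevenly recorded in, the AE tables

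*Combined protocol and SAP*

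**What the plan says.** The protocol sets the threshold for a laboratory AE in three places, and they differ.

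- **Section 3.2.1.1 (definition).** "An AE is any unfavorable and unintended sign (including an abnormal laboratory finding". No symptom, grade or clinical-significance condition is attached, and laboratory results are named as one basis for judging that an AE has occurred.
- **Section 3.2.4 (recording).** "Abnormal laboratory values will be recorded on the laboratory section of the eCRF and not in the AE section". Two sentences soften this: "Abnormal laboratory results leading to a clinical diagnosis will be reported with a clinical term by the investigator and recorded in the AE section", and "Abnormal laboratory results that meet the definition of an SAE should also be reported on an SAE form".
- **Table 1 and Section 2.6.9 (dose adjustment).** Under uncomplicated hematological AEs, Table 1 lists "Neutropenia Grade 3 or 4 upon observation" and the same for thrombocytopenia. For non-hematological AEs, only laboratory values without clinical significance are set aside.

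Section 5.10.1 builds the safety tables from treatment-emergent AEs: by preferred term and worst grade, treatment-related, Grade 3 or higher, leading to discontinuation, and SAEs. Section 5.10.2 handles laboratory data separately, with descriptive summaries, shift tables from baseline to maximum grade, and listings.

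Section 1.8 reports that the Grade 3 and 4 toxicities at 40 mg in Phase 1 occurred in 2 of 6 patients and were asymptomatic. One was a Grade 4 neutropenia treated with G-CSF. The other was an ALT rise: "The Grade 3 ALT elevation was also asymptomatic resolved with dosing interruption". Sections 2.6 and 3.4.1 single out neutropenia and transaminase elevation as the signals to watch.

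**The concern.** Safety is the secondary objective, and Section 2.3 measures it by the number of patients with AEs and their severity. The events that the plan most expects to monitor are laboratory findings that may cause no symptoms. Section 3.2.4 steers exactly these away from the AE section unless they reach a clinical diagnosis or the SAE definition.

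A site following 3.2.4 and a site following 3.2.1.1 or Table 1 could record the same event differently. With about 22 patients spread over 25 to 35 sites, most sites would contribute very few patients, so differences in reading would feed directly into the AE counts. Section 5.1 says the main analysis is meant for regulatory submission.

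Analysis cannot repair this afterwards. If the investigator never enters an AE record, there may be no causality judgment or link to a dose change for a later table to use.

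**Working it through.** The plan gives no figure to reproduce on this point. The check sets the rules side by side, traces the effect on the tables, and then does a small calculation for scale.

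**1. Example events under each rule**

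| Event | 3.2.1.1 | Table 1 / 2.6.9 | 3.2.4 |
|---|---|---|---|
| Asymptomatic Grade 3 ALT rise that interrupts dosing | AE | AE, if judged clinically significant | Laboratory page only, unless it leads to a clinical diagnosis or meets the SAE definition |
| Uncomplicated Grade 4 neutropenia given G-CSF | AE | AE on observation | Depends on whether the site treats neutropenia as a clinical diagnosis or as serious |
| Uncomplicated Grade 3 or 4 thrombocytopenia with slow recovery, study drug stopped | AE | AE on observation | Same dependence |
| Grade 1 laboratory change of no clinical significance | AE | Not an AE for dose adjustment | Laboratory page only |

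The first row is the clearest conflict. The second and third depend on site judgment. The fourth shows that 3.2.1.1 is itself broader than the other two rules, so changing 3.2.4 alone would not make them agree.

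**2. Effect on the tables**

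- The related, Grade 3 or higher and discontinuation tables in 5.10.1 are tables of TEAEs. An event that exists only on the laboratory page is not in them.
- Section 3.2.9 grades every laboratory abnormality, and 5.10.2 shows it in shift tables and listings. Grade is therefore kept. Section 5.10.2 plans no summary by causality, action taken or discontinuation.
- Section 5.10 promises to characterize the relationship to study therapy for laboratory abnormalities as well as AEs. Section 5.10.2 has no output that does so.
- Section 5.5.3 tabulates withdrawals due to AE. A patient stopped for a slow-recovering cytopenia could be counted there with no matching AE record.
- Follow-up after end of treatment (2.6.4, 3.2.2) applies to related AEs of Grade 2 or higher, so it also depends on an AE having been recorded.

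**3. Scale, for illustration only**

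Inputs: 2 of 6 Phase 1 patients at 40 mg with asymptomatic Grade 3 or 4 toxicity (1.8); planned enrollment of 22 (5.2). Assumption: the Phase 1 rate carries over.

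- Rate: 2/6 = 33.3%.
- Exact (Clopper-Pearson) 95% CI: lower limit = 2.5% quantile of Beta(2, 5) = 4.3%; upper limit = 97.5% quantile of Beta(3, 4) = 77.7%.
- Projected to 22 patients: 22 × 0.333 = 7.3; 22 × 0.0433 = 0.95; 22 × 0.7772 = 17.1.

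So about 7 of 22 patients, with a range of roughly 1 to 17, could have an event whose place in the AE tables depends on which section the site follows. This is not a forecast of missing events.

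**The case against.** The strongest reply is that little would be lost in practice, and several parts of it stand.

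- **Exceptions in 3.2.4.** The SAE route matters. Section 3.2.1.2 names blood dyscrasias without hospitalization among its examples of important medical events, so a Grade 4 neutropenia could be reported that way. Neither exception clearly reaches an asymptomatic ALT rise that interrupts dosing.
- **Clinical terms.** A site may reasonably enter neutropenia or thrombocytopenia as the AE term, and Table 1 invites it. Section 2.6.8 also treats prolonged Grade 4 neutropenia as a treatment-related AE. For cytopenias the risk is therefore uneven recording, not certain omission.
- **Data retained.** Graded shift tables and listings keep the values. Section 3.2.4 also says that relationship and countermeasures go on the eCRF. It does not say whether this covers laboratory-only entries, and no planned laboratory output uses it.

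Three stronger readings are tempting, and the documents do not support them.

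- A reader might infer that the drug's main toxicities would vanish from the AE tables. The documents do not call these its main toxicities. That is an inference from six patients and the monitoring emphasis, and the exceptions make loss possible rather than certain.
- A reader might take the safety endpoint in 2.3 ("laboratory tests results will be recorded and assessed by severity and association with study treatment") to require a causality judgment for every laboratory abnormality. The subject of that sentence is AEs, including those observed through laboratory tests, so it does not by itself contradict 3.2.4.
- A reader might infer that 5.10.1, with "those judged by the investigator to be related or likely related to HBI-8000", drops events rated Possible. Section 3.2.5 already handles Definite, Probable and Possible as related for reporting purposes. The wording is loose but removes nothing.

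**Conclusion.** Wrong as written, and inexpensive to correct. Section 3.2.4 cannot be reconciled with 3.2.1.1 or with the hematological rows of Table 1, and it applies a different test from the clinical-significance test in Table 1 and 2.6.9. Asymptomatic laboratory toxicities that interrupt or stop dosing could be missing from the TEAE, Grade 3 or higher, treatment-related and discontinuation tables, or recorded differently between sites. The clearest case is a Grade 3 ALT rise; uncomplicated neutropenia is a possible one. The graded values themselves are not lost.

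The size is uncertain. The figure of about 7 of 22 (roughly 1 to 17) assumes that a rate from six Phase 1 patients with non-Hodgkin's lymphoma applies here and that both kinds of event are exposed to the conflict. Reading it as the number who would be missing further requires every site to apply 3.2.4 literally and no event to meet an exception. That is the extreme case. The textual conflict does not depend on this projection.

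**What to change.** Reconcile 3.2.1.1, 3.2.4 and Table 1/2.6.9 into one recording rule. A laboratory abnormality would be entered as an AE, in addition to the laboratory page and with CTCAE grade and causality, when any of these holds:

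- the investigator judges it clinically significant;
- it is an event that Table 1 lists as an AE;
- it leads to a dose hold, reduction, discontinuation or treatment.

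The existing clinical-diagnosis and SAE provisions can stay. Section 3.2.1.1 should refer to the same rule, so that its unconditional definition no longer competes with it. A grade cut-off alone would not be enough, because it would leave 3.2.1.1 unreconciled.

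Optionally, define treatment-related in 5.10.1 by reference to 3.2.5 (Definite, Probable, Possible). This only aligns the wording.

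The cost is a few wording changes, a note to sites, some extra AE entries and less favorable AE counts. The change affects recording and analysis only. It alters no dose, dose-adjustment step or other clinical rule.

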### **3.2.5 Assessment of Causal Relationship to Study Drug**

The relationship of an AE to the study medication is graded as follows:

**Definite:**

- Distinct temporal relationship with the study drug
- Stops/improves when the study drug has been stopped
- Can reasonably be explained by known characteristics of the drug

**Probable:**

- Reasonable temporal sequence from the study drug administration
- Stops/improves when the study drug has been stopped
- Event cannot easily be explained by patient's clinical state or other factors

**Possible:**

- Reasonable temporal relationship with the study drug
- Event could have been produced by the patient's clinical state or other factors

**Unlikely:**

- Poor temporal relationship to the study drug
- Patient's clinical state is likely to have an association with the effect

**Unrelated:**

- Definitely not associated with the study drug administered

“Definite”, “Probable” and “Possible” events are regarded as AEs that cannot be denied a causal relationship to the study drug, that will be handled as “related to the study drug” for reporting purposes, and “Unlikely” and “Unrelated” events are regarded as AEs that can be denied a causal relationship to the study drug, that will be handled as “not related to study drug” for reporting purposes.

### **3.2.6 Intensity of Adverse Events**

The intensity of adverse changes in clinical signs or symptoms will be graded according to the CTCAE. For all other AEs not described in the CTCAE criteria, the intensity will be assessed by the investigator using the following categories:

**Grade 1:**

- Mild; asymptomatic or mild symptoms; clinical or diagnostic observations only; intervention not indicated

## **Grade 2**

- Moderate; minimal, local, or noninvasive intervention indicated; limiting age-appropriate instrumental activities of daily living (ADL). Instrumental ADL refer to preparing meals, shopping for groceries or clothes, using the telephone, managing money, etc.

## **Grade 3**

- Severe or medically significant but not immediately life-threatening; hospitalization or prolongation of hospitalization indicated; disabling; limiting selfcare ADL. Selfcare ADL refer to bathing, dressing and undressing, feeding self, using the toilet, taking medications, and not being bedridden

## **Grade 4**

- Life-threatening consequences; urgent intervention indicated

## **Grade 5**

- Death at least possibly related to the AE

### **3.2.7 Events Requiring Immediate Reporting**

#### ***3.2.7.1 Serious Adverse Events***

Adverse events classified as “serious” must be reported in timely fashion to comply with regulatory requirements. All suspected unexpected serious adverse reaction associated with the use of HBI-8000 will be reported to the regulatory authorities in accordance with the Guideline for Industry International Council for Harmonisation (ICH) E2A, Clinical Safety Data Management: Definitions and Standards for Expedited Reporting.

All SAEs must be recorded in the eCRF within 24 hours of investigator awareness of the event. In particular, if the SAE is fatal or life-threatening, notification to the sponsor must be made within 24 hours, irrespective of the extent of available AE information. In case the eCRF cannot be used by investigator to generate the SAE/Pregnancy form, a paper SAE/Pregnancy form will be used and will be faxed to [REDACTED]. Once the eCRF limitation is resolved, the investigator should enter all the information from the paper report into the eCRF as soon as possible.

[REDACTED]

This timeframe also applies to additional new information (follow-up) on previously forwarded SAE reports. For all SAEs, the investigator is obligated to pursue and provide information to the sponsor in accordance with the timeframes for reporting specified above. In addition, an investigator may be requested by the sponsor to obtain specific additional follow-up information in an expedited fashion. In general, this will include a description of the AE in sufficient detail to allow for a complete medical assessment of the case and independent determination of possible causality. Information on other possible causes of the

event, such as concomitant medications and illnesses must be provided. In the case of death, a summary of available autopsy findings must be submitted as soon as possible to the sponsor. All SAEs occurring in this study requiring expedited regulatory reporting will be evaluated, summarized, and reported to investigators. These SAEs must also be submitted in writing by investigators to the institutional review board (IRB).

